# 8.3. Safety Assessments

Safety assessments will be made on the SAF population.

### 8.3.1. Adverse Events

Overall summary for the following will be conducted.

- Subjects with at least one TEAE
- Subjects with at least one serious TEAE
- Subjects with at least one TEAE leading to study medication discontinuation
- Subjects with at least one treatment emergent AESI
- Subjects with TEAE leading to death

According to protocol, all fractures will be collected as adverse events of special interest (AESI).

The following summaries also will be conducted.

- TEAEs by SOC and PT
- Serious TEAEs by SOC and PT
- TEAEs Leading to Study Treatment Discontinued by SOC and PT
- Treatment Emergent AESI by SOC and PT
- TEAEs by SOC, PT and severity
- TEAEs by SOC, PT and relationship to study medication

Each of the summaries will be done at the subject level - multiple occurrences of the same event within a subject will be counted once in the summaries by SOC and PT; multiple occurrences of the same event within a subject will be counted once in the maximum severity category (severe > moderate > mild) and/or maximum drug relationship category (reasonable possibility/no reasonable possibility).

The following will be listed.

- TEAEs
- Serious TEAEs
- TEAEs leading to study medication discontinuation
- Treatment emergent AESI
- Death

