8.5 Withdrawal of Individual Subjects

A subject will be withdrawn if ANY of the following criteria are met:

- The subject wishes to withdraw from further participation
- The subject is significantly noncompliant with the Protocol
- Continuing in the study would be detrimental to the subject's safety in the opinion of the Investigator, eg, the subject experiences a pretreatment event (PTE) or an AE that requires early termination (ET) because continued participation poses an unacceptable risk to the subject's health, or the subject is unwilling to continue because of the PTE or AE
- Subjects who become pregnant during the study should be withdrawn from study treatment. Refer to Section 12.9 for necessary documentation and procedures for following up with the subject
- Subjects who develop:
 - Hypersensitivity reactions, such as anaphylaxis and moderate to severe infusion-related reactions.
 - Abnormal hematologic indices as below:
 - White blood cell count (WBC) < 3000/mm3 (< 3.0×10^9 /L) or absolute neutrophil count < $1.500/\mu$ L
 - Platelets < 100,000/μL
 - Hemoglobin < 8 g/dL

Note: If a subject has a decline of hemoglobin to < 9 g/dL, hemoglobin will be repeated within 2 weeks.

- ALT or AST > 5 times ULN
- ALT or AST > 3 times ULN sustained for more than two weeks
- ALT or AST > 3 times ULN AND total bilirubin > 2 X ULN or international normalized ratio > 1.5

Note: If a subject experiences elevated ALT or AST \geq 3 times ULN, liver tests (ALT, AST, bilirubin, ALP, gamma-glutamyl transferase, and creatinine kinase) will be repeated within 3 to 5 days.

In addition, a subject may be withdrawn at any time for reason(s) other than those listed here. Medical monitor should be notified for all withdrawals.

If a subject is withdrawn prematurely from the study, the date the subject is withdrawn from the study and the reason for withdrawal will be recorded in the electronic Case Report Form (eCRF).

In case of withdrawal of a subject, the ET assessments should be performed per Table 2.

Reporting events as a SAE must be considered in cases where the AE has led to a withdrawal or the withdrawal is for a safety reason and, therefore, may be medically important, in

accordance with Section 12.

Any unresolved AE or SAE will be followed up according to Section 12.10.

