11.3 Compliance

Study medication will be administered by according to the Protocol requirements, by designated qualified study personnel at the study site. The Investigator, or suitably qualified staff member, will supervise the administration of study medication and the exact time of dosing will be recorded in the subject's eCRF.

The prescribed dosage, dose duration, timing and mode of administration of study medication may not be changed. Any departures from the intended regimen must be recorded in the subject's eCRF.

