12.2 Adverse Events of Special Interest

AESIs will be collected for the following:

All bone fractures

All AESIs (including event management and evaluation) will be recorded and reported similar to SAEs as described in Section 12.8. MT-2990 does not have any hormonal effects and is not anticipated to have any impact on bone mineral density. However, this population has been exposed to other hormonal treatments prior to study entry, increasing the risk of osteoporosis and possible fractures.

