12.7 Recording and Reporting of Adverse Events

All AEs, regardless of the relationship to study medication, occurring from Day 1, will be obtained from a subject until the end of the Double-blind Treatment Period (Visit 9) or the withdrawal of the subject from the study will be recorded.

NOTE: Elective hospitalization or procedure/surgery planned before subject enrollment for a preexisting medical condition does not constitute an AE unless the underlying disease or condition worsens after Day 1.

All AEs will be recorded on an AE form in the eCRF. Reports should contain a description of the event, date and time of onset, date and time of resolution, severity, treatment required, relationship to study medication, action taken with the study medication, outcome and whether the event is classified as serious.

The Investigator will evaluate the severity of the AEs (as defined in Section 12.4) and will assess the causality between the AEs and the study medication (as defined in Section 12.5).

Pre-existing illnesses, which started prior to entry and are still ongoing at the start of the study, will not be considered AEs unless they worsen during the Double-blind Treatment period. Pre-existing conditions will be recorded as medical history.

If the Investigator becomes aware of any new safety information, or any safety information, which appears to be either study or study medication related after the Double-blind Treatment period, then they must notify the Sponsor immediately. This information does not require reporting of an AE on the eCRF, but should still be communicated to the Sponsor.

12.8 Recording and Reporting of Serious Adverse Events or Adverse Events of Special Interest

All SAEs occurring from the time written ICF is obtained from a subject until the end of the Double-blind Treatment Period or the withdrawal of the subject from the study must be reported to the Sponsor or the designee using the SAE/AESI Form in Clinical Study within 24 hours of the Investigator becoming aware of the SAE. All SAEs and AESI must also be entered in the AE section of the eCRF within 24 hours.

SAE report should be completed as thoroughly as possible, including an assessment of causality. All such reports will identify subjects by unique code numbers assigned to the study participants, rather than by the subjects' names, personal identification numbers, or addresses.

The reporting contact for SAEs/AESI is as follows:

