# 3.3. Determination of Sample Size

Power analysis for sample size calculation was performed under 2-sample t-test at the 5% level of significance to identify significance of the difference between MT-2990 and placebo on the mean change from Baseline through Week 16 in nonmenstrual pelvic pain. A total of 28 subjects per arm will provide at least 80% power for detecting a clinically meaningful difference (placebo versus treatment) of -0.5 in the mean change from Baseline in nonmenstrual pelvic pain and a standard deviation (SD) of 0.65,

As this study is exploratory study (proof of concept study), multiplicity for multi-endpoint is not considered. Assuming a drop-out rate of 25%, a total of 76 subjects (38 subjects per arm) are planned to be randomized in this study.

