# 4.3. Data Monitoring Committee (DMC)

An independent DMC, composed of experts in the management of subjects with the disease under study will be established for MT-2990-A01 according US FDA guidance. An independent biostatistician will be assigned to the DMC to maintain the integrity of the study blind and provide safety data at regular predefined intervals during the study and provide the interim safety assessments to the DMC.

The primary purpose of this committee will be to review safety data for the protection of subject safety (including infusion site reactions, hypersensitivity and immune system disorders such as allergic reaction, anaphylaxis, cytokine release syndrome, etc).

There will be 3 interim safety assessments as described in section 4.1. The planned interim safety assessments will be conducted to determine whether the study will be stopped due to safety concerns.

A DMC charter will outline the scope and key responsibilities, timing of reviews, communications between the DMC and the Sponsor, and recommendations and action rules for

the study.

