#### 6.2. Statistical Tests

Unless otherwise specified, all formal statistical tests of treatment effects will be done at two-sided significance level of 0.05. Point estimates will be accompanied with two-sided 95% confidence intervals where applicable.

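### SAP 8.3.1 has no grouped or infusion-timed table for infusion and hypersensitivity reactions, although the DMC remit and the withdrawal criteria both name them

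*SAP*

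**What the plan says.** **Where these reactions are named.** SAP 4.3, matching Protocol 15.3, describes the DMC's task: "The primary purpose of this committee will be to review safety data for the protection of subject safety (including infusion site reactions, hypersensitivity and immune". The parenthesis goes on to disorders of the immune system, with anaphylaxis and cytokine release syndrome among the examples. The interim assessments are to inform whether the study stops for safety. Protocol 8.5 lists as a withdrawal ground: "Hypersensitivity reactions, such as anaphylaxis and moderate to severe infusion-related reactions". Protocol 12 asks for about an hour of observation after each infusion. It also provides an instruction sheet that draws subjects' attention to infusion-related events and infections.

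**What is tabulated.** SAP 8.3.1 has overall rows for any TEAE, serious TEAEs, TEAEs leading to discontinuation of study medication, special-interest events and deaths. Tables by organ class and preferred term follow, including splits by severity and relationship. The special-interest group is fractures: "According to protocol, all fractures will be collected as adverse events of special interest (AESI"). Protocol 12.2 says of the drug: "MT-2990 does not have any hormonal effects and is not anticipated to have any impact on bone mineral density". It justifies the fracture group by the population's earlier hormonal treatment.

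**What is collected.** For adverse events, Protocol 12.7 states: "Reports should contain a description of the event, date and time of onset, date and time of resolution, severity". For dosing, Protocol 11.3 states that "the exact time of dosing will be recorded in the subject's eCRF".

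**The concern.** The reactions that the protocol watches for at each infusion have no table of their own. The one special-interest table covers an event that the drug is not expected to cause. A single reaction can be reported as, for example, flushing, itching, nausea or breathlessness. Those symptoms fall under different preferred terms and organ classes, and the planned tables count each separately.

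Safety and tolerability is a secondary objective. Protocol 7.2.1 describes one earlier clinical study, of single doses in healthy men. This trial gives women up to four doses (SAP 7.1.1.2), so reactions on repeat exposure are a new question. Neither a count of women with a reaction by arm nor a count by infusion number can be read from the planned tables.

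The vital-sign tables do not clearly fill the gap. Protocol 10.18.2 requires readings at about 15, 30 and 60 minutes after infusion, but the visible text of SAP 8.3.3 and 9.3 refers only to analysis visits.

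**Working it through.** **1. The plan's own number.** The stated basis is "Power analysis for sample size calculation was performed under 2-sample t-test at the 5% level of significance", with a difference of 0.5, SD 0.65 and at least 80% power. SAP 6.2 sets the sidedness: "all formal statistical tests of treatment effects will be done at two-sided significance level of 0.05".
- Normal approximation: n = 2 × (1.960 + 0.842)² × 0.65² / 0.5² = 26.5, so 27 per arm.
- Exact noncentral t: power is 79.2% at 27 and 80.7% at 28, so 28 per arm is reproduced.
- Dropout of 25%: 28 / 0.75 = 37.3, so 38 per arm and 76 in all.

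The sample size is sound and not in question. It supplies the 38 per arm used below; the safety population is everyone dosed.

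**2. One pooled row against several split rows.** With equal arms of size n, k events on one arm and none on the other, the two-sided Fisher p-value is 2 × C(n,k) / C(2n,k). At n = 38:

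| Women with event, MT-2990 v placebo | % | p |
|---|---|---|
| 1 v 0 | 2.6 v 0 | 1.00 |
| 2 v 0 | 5.3 v 0 | 0.49 |
| 5 v 0 | 13.2 v 0 | 0.054 |
| 6 v 0 | 15.8 v 0 | 0.025 |

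Six affected women therefore appear as one row of 6 v 0 if pooled. They appear as three rows of 2 v 0 if spread evenly over three organ classes, and as six rows of 1 v 0 if every woman has a different term.

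**3. How often each display would show an imbalance.** The documents give no reaction rates and no number of terms, so the rates and the even split over four terms are assumptions. The yardstick is Fisher p ≤ 0.05 with more events on MT-2990. Its probability is the sum of binomial probabilities over all outcomes meeting that condition. For the split display it is 1 − (1 − q)⁴, where q is the probability for one term and terms are treated as independent.

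| Per arm | Assumed total rate | Pooled row | Any of four term rows |
|---|---|---|---|
| 38 | 10% v 2% | 9% | 0.1% |
| 38 | 20% v 2% | 60% | 4% |
| 38 | 20% v 0% | 80% | 4% |
| 38 | 30% v 4% | 84% | 17% |
| 19 | 20% v 2% | 24% | 0.7% |
| 10 | 20% v 2% | 2.7% | under 0.1% |

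For 20% v 2% at 38 per arm, q = 0.0091 and 1 − (1 − 0.0091)⁴ = 0.036.

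**4. The interim assessments.** The first is at 20 subjects, about 10 per arm. The second and third are at 50%, which is 38 subjects or about 19 per arm. Even pooled, 3 v 0 of 19 gives p = 0.23 and 2 v 0 of 10 gives p = 0.47. Pooling at those looks gives a readable count, not a formal signal.

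**5. Can the tables be built?** Yes. Onset date and time and dosing time are both recorded (Protocol 12.7 and 11.3), so time from infusion can be derived.

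**The case against.** The other side has several good points, and most limit the size of the concern.

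- **DMC purpose.** A reader might infer that infusion and hypersensitivity reactions are the DMC's main purpose. The text does not say so. The purpose is safety review in general, and these reactions are examples in an open-ended parenthesis.
- **Existing pooling.** A reader might infer that fractures are the only thing pooled. They are the only special-interest group, but the overall rows pool all terms and the organ-class rows pool within a class. Reactions that trigger withdrawal should also reach the discontinuation row and listing. That row mixes them with other causes, and its breakdown is again by organ class and term. Milder reactions need not appear there.
- **Splitting is not documented.** Investigators may record the reaction as one diagnosis. Protocol 12.6 prefers a diagnosis only over abnormal laboratory values or assessments, so it does not settle how symptoms are recorded. Splitting is a risk, not a fact.
- **Worst case.** Six women with six different terms is an extreme, and 6 v 0 is the smallest count against zero below 0.05. SAP 8.3.1 plans no test on adverse events, so 0.05 is a yardstick used here, not the plan's standard.
- **Other routes.** The DMC gets adverse event lists monthly and can ask for more (Protocol 13.1). It works to a charter not among the documents, which may contain grouped displays. With 76 women, reading listings line by line is feasible. This answers much of the concern for the DMC, but it does not put a prespecified table in the final report.

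**Conclusion.** The point holds as a worthwhile, low-cost improvement. In the visible text, fractures are the only special-interest group, and no table groups infusion or hypersensitivity reactions or places events in time from infusion. Content is missing around SAP 7.1.3.1, but Protocol 12.2 and SAP 8.3.1 also name fractures only.

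The consequence is conditional. If symptoms are coded to different terms and classes, a modest imbalance, mainly of milder reactions, may go unseen in the Week 16 tables. On assumed rates of 20% v 2% over four terms, a pooled row would meet the yardstick in 60% of trials, against about 4% for any single term row. At 10% v 2% even the pooled row would do so in only 9%. These figures rest entirely on the assumed rates, the even split and independence between terms.

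Two stronger conclusions are not supported. One is that the planned tables cannot address safety and tolerability: listings, severity and relationship tables and the discontinuation row all remain. The other is that the DMC will miss a signal at the interims: it has other sources, and pooling adds little formal power at 10 or 19 per arm.

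**What to change.** Add two tables to SAP 8.3.1, for the Week 16 analysis and any interim safety assessment still to come:

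1. Subjects with at least one TEAE starting during an infusion or within a stated window after its start, by arm and infusion number (1 to 4), derived from recorded onset and dosing times. Label the window (for example 24 hours) as an analysis convention; the documents set none.
2. Subjects with at least one hypersensitivity or infusion-reaction term, by arm, from a term list tied to the MedDRA version in SAP 7.1.3.1 and fixed before the sponsor is unblinded at the Week 16 lock.

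Present both as descriptive counts and percentages, without tests, and keep the fracture table. Fixing the list before the first interim assessment is probably no longer possible: the SAP rests on the amendment of 04 March 2020, and the synopsis had estimated last-subject completion in February 2020.

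The cost is two derived tables and one agreed term list, with no new data or visits. The downside is that some unrelated same-day events will be counted, in both arms.

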# 8.3.2. Laboratory Tests

Absolute values and changes from baseline will be summarized for the following laboratory tests parameters.

Laboratory Test	Parameters		
Hematology	Hemoglobin*, Hematocrit*, Platelet count*, Red blood cell (RBC)		
	count*, Reticulocyte count*, Mean corpuscular hemoglobin (MCH),		

	Mean corpuscular hemoglobin concentration (MCHC), Mean corpuscular volume (MCV), White blood cell (WBC) count and differential
Biochemistry	Alkaline phosphatase (ALP) *, Aspartate aminotransferase (AST) *, Alanine aminotransferase (ALT) *, Gamma-glutamyl transpeptidase (GGT) *, Potassium*, Sodium*, Chloride*, Inorganic phosphate, Glucose*, Urea, Bilirubin (direct and total) *, Cholesterol*, Triglycerides*, High density lipoprotein-cholesterol (HDL-C) *, Low density lipoprotein-cholesterol (LDL-C) *, Protein (total) *, Albumin*, Creatine kinase*, Creatinine*
Coagulation	Prothrombin time*, International normalized ratio*, Activated partial thromboplastin time*
Urinalysis	Specific gravity, pH*, protein*, glucose*, ketones*, urobilinogen*, haemoglobin

Only the parameters with \* will be summarized for interim safety assessment.

Shift table for urinalysis will be generated if it is needed.

All data will be listed.

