10.18.6 Total blood volume

The approximate total blood volume taken per subject is given in Table 5.

Table 5 Blood Volumes

Procedure	Sample volume (mL)	No. of samples	Total volume (mL)
Hematology	3.0	10	30.0
Biochemistry	4.0	10	40.0
Coagulation	3.0	10	30.0
PK	2.5	9	22.5
Measurement of anti-MT-2990 antibody	5.0	5	25.0
Biomarker (in serum)	7.0	5	35.0
	•	Overall total	182.5

Additional or repeat safety laboratory samples may be taken during the study if required by the Investigator.

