13 DATA COLLECTION AND PROCESSING

13.1 Data Monitoring Committee:

An independent Data Monitoring Committee (DMC) will convene to review safety data when:

- a. 20 subjects are randomized and have completed the Week 2 visit
- b. 50% of subjects are randomized and have completed the Week 4 visit
- c. 50% of subjects are randomized and have completed the Week 16 visit

The independent DMC members will receive the list of AEs and SAEs every month and can request further information. All SUSARs will be reported in real time to the independent DMC, per expedited regulatory reporting timeframes (eg, 7 and 15 days). All subjects who are enrolled and received study medication will be included in the safety evaluations by the independent DMC at Weeks 2, 4, and 16.

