# (2) Safety

Analysis Visit	Apply to		
	Laboratory Tests	Vital Signs	12-Lead ECGs
Baseline	X	X	X
Week 1	X	X	
Week 2	X	X	·
Week 4	X	X	
Week 8	X	X	
Week 12 (EOT)	X	X	
Week 13	X	X	
Week 16	X	X	X
Week 27			
Week 38 (EOS)			

Unscheduled visits will not be displayed in by-visit summary tables but will be included in the data listings.

In by-visit summary tables for interim safety assessment, limited analysis visits will be reported. The first interim safety assessment will report baseline to Week 2. The second interim safety assessment will report baseline to Week 4. The third interim safety assessment will report baseline to Week 16. All visit will be included in the data listing.

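### White cell and neutrophil counts are the only laboratory quantities with a withdrawal limit that the SAP leaves out of the interim safety tables

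*SAP*

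**What the plan says.** SAP 8.3.2 lists the laboratory parameters to be summarised as absolute values and changes from baseline. It then states that only those with an asterisk "will be summarized for interim safety assessment". The hematology row ends with "Mean corpuscular volume (MCV), White blood cell (WBC) count and differential", and neither item has an asterisk. The same section says that all laboratory data will be listed.

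Protocol 8.5 gives the laboratory findings that lead to withdrawal of a subject. The hematologic ones begin with "White blood cell count (WBC) < 3000/mm3" or a low absolute neutrophil count, followed by platelets and hemoglobin. The hepatic ones use ALT and AST, alone or combined with "total bilirubin > 2 X ULN or international normalized ratio > 1.5".

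On the purpose of the interim reviews, SAP 4.3 says that the "interim safety assessments will be conducted to determine whether the study will be stopped due to safety concerns". SAP 9.3, part (2) Safety, limits the visits shown in the interim tables but says of the listings: "All visit will be included in the data listing". Protocol 13.1 adds that the DMC members will "receive the list of AEs and SAEs every month and can request further information".

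**The concern.** The withdrawal list is the protocol's own statement of which laboratory changes are serious enough to end a subject's participation. One would expect each quantity on it to be tabulated when the DMC considers stopping the study. All are, except white cells and neutrophils, and the SAP gives no reason in 4.1, 4.3, 8.3.2, 9.3 or section 10.

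The omission falls on a relevant system. MT-2990 blocks IL-33, which Protocol section 5 describes as acting on both innate and adaptive immunity. Protocol 15.3 and SAP 4.3 name immune system disorders within the DMC's primary purpose. Protocol section 12 asks subjects to report infections in particular. Protocol 7.2.1 records one earlier clinical study, of single doses in healthy men, so the effect of repeated dosing on leukocytes in this population is not yet described.

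What is at stake is early sight of a group-level fall (or rise) in leukocytes or neutrophils. If no subject crosses a limit and no value is judged clinically significant, there is no withdrawal and no adverse event, and no interim table specified in the SAP would show the shift.

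**Working it through.** The plan states no figure to reproduce; the check is a count and a cross-match.

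**1. Marked entries in the SAP 8.3.2 table**

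| Group | Entries | Marked | Unmarked |
|---|---|---|---|
| Hematology | 9 | 5 | MCH, MCHC, MCV, WBC and differential |
| Biochemistry | 19 | 17 | inorganic phosphate, urea |
| Coagulation | 3 | 3 | none |
| Urinalysis | 7 | 5 | specific gravity, urine hemoglobin |

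Entries: 9 + 19 + 3 + 7 = 38. Marked: 5 + 17 + 3 + 5 = 30. Unmarked: 38 − 30 = 8.

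**2. Laboratory quantities with a limit in Protocol 8.5, matched to the mark**

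| Quantity | Interim summary in SAP 8.3.2 |
|---|---|
| Hemoglobin (blood) | yes |
| Platelets | yes |
| ALT | yes |
| AST | yes |
| Total bilirubin | yes |
| INR | yes |
| WBC | no |
| Absolute neutrophil count (within the differential) | no |

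Covered: 6 of 8. The two gaps share one table entry and one withdrawal criterion. The other seven unmarked entries have no limit in Protocol 8.5.

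**3. Is brevity the explanation?** Marks with a withdrawal limit: 6. Marks without one: 30 − 6 = 24. These 24 include cholesterol, triglycerides, urine ketones and urobilinogen, so the interim set is not a short list from which WBC was dropped to save space.

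**4. What is missing at each review** (laboratory column of the visit table in SAP 9.3)

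- First review, Baseline to Week 2: Baseline, Weeks 1 and 2 = 3 visits.
- Second review, Baseline to Week 4: the above plus Week 4 = 4 visits.
- Third review, Baseline to Week 16: the above plus Weeks 8, 12, 13 and 16 = 8 visits.

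**5. Reading the listings instead.** The third review takes place when 50% of subjects have completed Week 16, which is 0.50 × 76 = 38. With complete visits these subjects contribute 38 × 8 = 304 WBC values, before the differential. Individual low values can be found in such a listing; a modest shift in the mean change from baseline is hard to see.

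**6. Could the mark have been lost in reproduction?** Four entries stand last in their cells. Creatinine and activated partial thromboplastin time keep their marks; WBC and differential and urine hemoglobin have none. That comparison settles nothing alone. But all 30 marks elsewhere survive, and MCH, MCHC and MCV, next to WBC, are also unmarked. A true omission is the more likely reading, and the source SAP would confirm it at once.

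**The case against.** The strongest reply is that nothing in the documents ties the interim tables to the withdrawal list. With 24 of 30 marks on parameters without a limit, the limits were plainly not the selection rule, and the SAP explains none of its marks, not just this one. The limits apply to individuals, whereas a summary of means does not show who crossed one; listings do, and WBC is listed. The first review is triggered by 20 subjects and the later two by about 38, so the listings can be read. The investigator assesses all laboratory data (Protocol 10.18.5), clinically significant values become adverse events (Protocol 12.6), the medical monitor is told of withdrawals (Protocol 8.5), and the DMC can ask for more. Its charter may already require a WBC table. Finally, the SAP rests on the amendment of 04 March 2020, while the protocol synopsis expected the last subject to complete in February 2020, so some or all reviews may already have taken place.

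Much of this stands, and it keeps the point small. The data are not withheld from the DMC, and the timing may limit the benefit. It does not remove the gap. Adverse events, withdrawals and listings capture individual abnormalities, and a request from the DMC requires that someone first suspects a signal. The same listings and reporting exist for hemoglobin, platelets, liver tests and INR, yet the SAP tabulates those. The summaries also include the minimum (SAP 6.1), so a WBC table would show how low values had reached as well as any shift in the mean.

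**Conclusion.** The concern holds, as a minor point. Of the eight laboratory quantities with a withdrawal limit, WBC and absolute neutrophil count are the only two without an SAP-specified interim summary, and the SAP does not say why. The gap covers 3, 4 and 8 visits at the first, second and third reviews.

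The conclusion concerns the tables specified in the SAP only. It assumes that the asterisks in the SAP table are reproduced correctly and makes no claim about the DMC charter, which is not among the documents. The effect is confined to interim monitoring, since the final analysis summarises WBC and differential. The withdrawal limits themselves are not questioned.

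**What to change.** In SAP 8.3.2, add the asterisk to the white blood cell count and differential entry, at least for total WBC and absolute neutrophils. Absolute values and changes from baseline would then be summarised at each interim safety assessment for the visits given in SAP 9.3. If the charter or the DMC table shells already include these rows, the mark brings the SAP into line with them.

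The cost is one mark and a few more rows per interim table. Protocol Table 5 already plans 10 hematology samples per subject ("The approximate total blood volume taken per subject is given in Table 5"), and the values are already listed, so no procedure or sample is added. The documents do not show which reviews preceded this SAP version; the change applies to those still to come.
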